1.0 Background

Terminology and General Benefits

Palliative care (PC) is specialized medical care focused on providing patients with relief from the symptoms, pain, and stress of serious or life-limiting illness, regardless of diagnosis, by anticipating, preventing, and treating suffering. The goal is to improve quality of life for both the patient and the patient's family. Palliative care is appropriate at any age and at any stage in a serious illness. It is intended to be provided together with curative treatment, and includes intensive focus on symptom and pain management, psychosocial support, and assistance in advance care planning.¹

In some studies, palliative care integration has been shown to improve patient quality of life (QOL), sleep quality, and spiritual well-being; reduce depressive symptoms, healthcare costs and utilization, and aggressive interventions at the end of life; increase participation in advance care directives, and even increase lifespan.^{2,3} A recent phase 3 randomized controlled PC trial in lung cancer patients showed that although fewer patients in the early palliative care intervention arm received aggressive end-of-life care (33% vs 54%), median survival was longer compared to patients who received standard of care alone (11.6 months vs 8.9 months).² Greater use of palliative care may also decrease end of life care costs in Medicare patients, particularly important to the national health care system⁴ as 30% of Medicare resources are expended on the 5% of beneficiaries who die each year.⁵ In an analysis of more than 5000 patients from 8 hospitals, PC involvement was associated with a cost savings of \$1,696 per admission for patients who survived hospitalization and \$4,908 per admission for patients who did not survive hospitalization.⁵ However, there are a paucity of PC efficacy data from randomized controlled trials.

A meta-analysis of palliative care trials found 22 randomized controlled studies with 14 of these interventions being of palliative intent and only 8 utilizing a specialized palliative care intervention. Overall, participants receiving palliative care showed improvements in QOL (5 out of the 7 trials which examined QOL as a primary outcome), increased satisfaction with care (7 out of the 10 trials which examined patient and caregiver satisfaction with care), and improved *coping* with physical symptoms (two trials that examined perceived symptom distress), with mixed findings in physical and psychological symptom improvement. These mixed findings may be due to methodological issues including small sample sizes, contamination of the control group, recruitment bias, and inadequate statistical power.⁶ There is a need for methodologically sound, randomized controlled trials examining specialized PC interventions, and in particular, there is a need to explore benefits of PC in patient populations with non-malignant, high mortality disease states such as cirrhosis, congestive heart failure, and emphysema.

Palliative Care for Hepatic Patients

Chronic liver disease and cirrhosis is the 12th leading cause of death in the United States.⁷ Patients with End Stage Liver Disease (ESLD), a progressive illness synonymous with decompensated cirrhosis, advanced liver disease, and liver failure⁸, face many complications and a variety of health symptoms including the development of ascites, variceal hemorrhage, hepatic encephalopathy, hepatocellular carcinoma, cognitive decline, fatigue, pruritus, malnutrition, pain, and renal impairment.^{9,10} Many cirrhotic patients face financial, emotional, and social problems relating to the stigma of liver disease,¹⁰ and QOL is often decreased due to physical and psychological symptoms.⁸ For patients with decompensated cirrhosis, liver transplantation is the only cure. 15,027 candidates were registered on the waiting list for liver transplant in the US as of December 31, 2013.¹¹ As hope for a transplant and cure is foremost in the mind of these patients, it is not surprising that palliative care opportunities may be overlooked. However, many patients are not candidates for transplantation, and those on the waitlist may never undergo transplantation or may have considerable wait time. In 2013 1,767 patients died while on the waiting list and 1,223 patients were removed due to being too ill to undergo transplant. Of the 5,921 patients who received a liver

transplant, 53.2% were on the waitlist for 3 months or longer and 21.1% for more than 1 year prior to transplant.¹¹ Even for those who undergo successful transplant, the symptom burden of cirrhosis warrants intervention.

In one retrospective study of 102 adult patients at a university hospital site who were either removed from the waiting list for liver transplant or were declined transplant, patients experienced significant symptoms including pain (65% of patients), nausea (58%), lack of appetite (49%), dyspnea (48%), anxiety (36%), and depression (10%). However, only 11% of patients were referred for palliative care, and only 28% had do-not-resuscitate (DNR) status in their chart.¹² Palliative care is often disregarded until hope of liver transplantation is lost, which may be in the last week or two of life. We hypothesize that offering both PC and disease-directed therapies simultaneously at the time of presentation to an inpatient hepatology service will delay or reduce hospital readmissions while maintaining or improving quantitative and qualitative measures of quality of life and end of life care.¹³

There is potential benefit to introducing palliative care earlier in the course of illness for patients with chronic liver disease. For some patients with cirrhosis, palliative care has been shown to improve physical and emotional symptoms. In a recent observational study, Baumann et al found that for patients with ESLD on the waiting list for liver transplant, an early PC intervention counteracted the progression of worsening symptoms and significantly improved pruritus, appetite, anxiety, depression, fatigue, and well-being.¹⁴

In addition to quality of life, hospital utilization for hepatic patients is of particular concern. Hospital admission rates and the economic burden of treating these patients have continued to rise.¹⁵ In a study of 402 patients with decompensated cirrhosis who were admitted to hospital, 78% of patients had at least one readmission, with 14% of these patients readmitted within 1 week after discharge at a mean cost of \$25,898 per readmission. Another 37% of these patients were readmitted within 1 month after discharge at a mean cost of \$20,581 per admission. Of these, 22% were determined to be possibly preventable admissions.¹⁶

Palliative Care interventions have been shown to reduce hospital utilization for some liver transplant service patients. Lamba et al conducted a prospective observational study comparing outcomes before and after structured palliative care program integration in the surgical intensive care unit for liver transplant service patients. After program implementation, goals of care discussions during physician rounds increased significantly (from 2% to 39% of patient-days), and the mean length of stay in the SICU decreased by 3 days for patients who died and by 4 days for patients who survived. Although mortality rates were similar pre- and post- program implementation, DNR status significantly increased in those who died from 52% pre-implementation to 81% post-implementation. DNR status was also instituted earlier, decreasing from 38 days after admission to 19 days after admission.¹⁷ Palliative care, once understood and integrated, has the potential to improve clinical outcomes, improve patient's quality of life, and reduce cost. But *when* to integrate the services, *how* to integrate services, and *for which* patients, is not well established.

Resistance and Conceptual Barriers

Even with its reported benefits, palliative care remains misunderstood and underutilized. Seventy percent of Americans describe themselves as “not at all knowledgeable” about palliative care.¹⁸ A majority of barriers to PC reported by patients were described either as a lack of referral by the doctor or lack of awareness in general about options related to palliative care. Data from a national public opinion survey of 800 adults commissioned by the Center to Advance Palliative Care showed 70% of people surveyed were totally unfamiliar with the term “palliative care” and the availability of the types of services it provides.¹⁹ When compared to palliative care, ‘supportive care’ has been associated with better understanding, more favorable impressions, and higher future perceived need.¹ In addition to the lack of understanding among patients, many healthcare professionals consider palliative care to be synonymous with end-of-life care. Approximately half of MDs in one study believed the purpose of PC is inconsistent

with cure and only appropriate when cure is no longer the goal.²⁰ This is unfortunate, given palliative care has been shown to prolong survival³ and decrease distress.²¹

Initiation of palliative care discussions with patients may depend on diagnosis rather than prognosis. One study found physicians were more inclined to discuss end of life decisions with patients who had cancer or HIV than patients with cirrhosis even when the prognosis was the same. Data from a multi-site study of 317 patients showed that patients with HIV or lung cancer had documentation of DNR orders more frequently than patients with cirrhosis, even after controlling for hospital, functional and mental status, severity of illness, and survival prognosis. DNR orders were present for 52% of patients with HIV, 47% of patients with lung cancer, 16% of patients with cirrhosis and esophageal varices, and 4% of patients with congestive heart failure. Only 8 out of the 51 patients with cirrhosis had DNR orders documented, and patient preference for this was documented in only 1 out of the 8 cases.²² The illness trajectory of patients with liver disease may differ compared to other types of organ failure (e.g., patients may experience periods of symptom improvement dependent on treatment of liver disease, i.e. alcohol cessation, antivirals therapy, low-sodium diet); however, “prognostic paralysis” should not delay palliative care.¹⁰

2.0 Rationale and Specific Aims

We will conduct a randomized, controlled study to evaluate the effectiveness of a systematic comprehensive palliative care intervention on patient outcomes in hepatology patients with poor prognosis. Our specific aims are to:

- 1) **Assess the impact of systematic, comprehensive palliative care services compared to usual hepatic care on time to first hospital readmission within 1-year post randomization.**
- 2) **Assess the impact of systematic, comprehensive palliative care services compared to usual hepatic care on other hospital utilization variables (including days alive out of hospital within 6-months post randomization, total days in hospital and ICU within 1-year post randomization, number and cost of hospital admissions within 1-year post randomization, median length of stay per admission, number of transfers to hospice within 1-year post randomization, time to hospice placement, and survival).**
- 3) **Assess the impact of systematic, comprehensive palliative care services compared to usual hepatic care on quality of life.**
- 4) **Assess the impact of systematic, comprehensive palliative care services compared to usual hepatic care on patient satisfaction and caregiver stress and satisfaction.**
- 5) **Evaluate the fidelity of the palliative care intervention and assess the generalizability of implementing a large-scale Palliative Care program.**

3.0 Preliminary Data

The term ‘Palliative Care’ is not well understood. The current study team conducted a pilot survey of ResearchMatch²³ participants which shows 81% of surveyed patients with chronic disease have heard of the term “palliative care” but they have variability in understanding the definition (See **Figure 1**).

[figure not shown]

Figure 1. Response to pilot survey question, “What does palliative care mean to you?” Data collected from 572 participants via ResearchMatch.

Confusion surrounding the association of palliative care with hospice and active dying may prevent conversations from being initiated by patients or providers, thereby perpetuating the cycle of confusion. One potential concern with introducing palliative care earlier in the disease trajectory is the assumption that patients would prefer to avoid discussing end of life care or may feel as if their treatment team is “giving up.” However, when 444 patients with chronic disease were asked in a separate ResearchMatch survey “Would you want to know your prognosis if you had less than six months to live?” 97% of patients responded yes, and 100% of the 91 patients with liver disease responded yes. For the 91 patients with liver disease who were surveyed, the majority of patients responded they would prefer to hear this prognosis from a health professional rather than a loved one (see **Figure 2**).

[figure not shown]

Figure 2. Response to survey question, “If your doctors believed you had less than six months to live, who would you want to hear this information from?” Data collected from 91 participants with liver disease via ResearchMatch.

5.0 Participant Selection

Approximately 400 adult hepatology patients with poor prognosis (identified by the ‘surprise question’ see below) will be randomized to receive either usual hepatic care (control group, N=200) or usual hepatic care with comprehensive palliative care services (intervention group, N=200). Any Vanderbilt patient admitted to the primary inpatient service of one of the study hepatologists with limited life expectancy may be eligible for participation. We expect a participation rate of ~75% (based on the participation rate of a similar study conducted by [name]), and no more than 10% of patients excluded based on eligibility criteria. We are powered to detect a 13% difference in readmission rate between treatment arms with 400 participants, assuming equal mortality across arms (see section 8.0, Statistical Analyses). As this is an internally funded study, we will have flexibility to enroll patients past the the accrual goal of 24-months in order to enroll 400 participants if necessary.

Inclusion Criteria:

- Inpatient at Vanderbilt University Medical Center with advanced liver disease, whose treating hepatologist indicates a ‘No’ response to the question, “Would you be surprised if this patient died within 1 year?”

Exclusion Criteria:

- Age < 18 years
- Inability to give written informed consent (patient or surrogate decision-maker)
- Inability to respond to questions in English
- Treating hepatologist denies permission to enroll
- Receiving hepatology care at non-Vanderbilt sites (to ensure appropriate follow-up)

Recruitment

Potential patients will be identified within StarPanel using hepatology service codes and/or attending physician name. Patients’ electronic medical records will be manually reviewed by study personnel to confirm preliminary eligibility. Once preliminary eligibility is established, the treating hepatologist will receive a prompt via email with a REDCap survey link to respond to the question, “Would you be surprised if this patient died within 1 year?” The ‘surprise question’ has been used in a variety of patient populations for prognosis and to evaluate appropriateness for palliative care^{25,26} and has shown specificity (69.3%) and

sensitivity (83.6%) with a positive predictive value of 83.8% and negative predictive value of 69.0% when correlated to one-year mortality rate as applied by general practitioners in an oncology setting.²⁷ The REDCap survey will contain the patient's name and medical record number for physician reference (**Appendix A**). If the treating physician indicates a 'No' response, the patient will be considered for inclusion into the study. On the same survey, the hepatologist will confirm the patient may be approached for consent and randomization into the study. The study team will maintain a Pre-Screening Log within REDCap to track patients who are reviewed for eligibility.

Consent Procedures

Appropriate patients will be approached by a study coordinator (SC) on the inpatient unit. The SC will provide a verbal description of the study and will inform potential participants that participation is voluntary, and if they enroll, they may withdraw from the study at any time, for any reason, before it is completed. Study staff will access the REDCap survey containing the most recent IRB approved e-consent document via portable electronic device (iPad) or computer. Study staff will review the information with the participant, and give the subject ample time to ask questions and have their questions answered. Written informed consent will be documented on the e-consent document via a typed signature. If there are technical issues, difficulty accessing the e-consent electronically, or if the patient prefers, a paper consent form will be used.

The patient's surrogate decision-maker will also be approached to provide consent for the study. The same process for obtaining written informed consent from the patient applies to the surrogate decision maker. He/she will indicate consent to allow the patient to participate via typed signature on the surrogate e-consent form or handwritten signature on the paper surrogate consent form. If the surrogate decision-maker is not present on the unit, the SC will contact the surrogate by telephone, describe the study, and will send an email containing the REDCap survey web link to the e-consent form. The email will also contain contact information (email and phone) of a member of the key study personnel for surrogate decision-makers to contact with questions prior to signing the e-consent. The SC will verbally review the study and e-consent form, and the surrogate decision-maker will sign the e-consent prior to enrollment.

If the patient does not have the capacity to give written informed consent due to his/her current health state, the surrogate will provide written informed consent prior to the patient's enrollment in the study. The patient will be re-evaluated periodically for the capacity to give consent. The SC will confirm with the treating hepatologist if the patient is capable of providing written informed consent while inpatient. If the patient is found capable, the study coordinator will obtain written informed consent from the patient. If the patient is found to be capable, but is discharged prior to providing written informed consent, the study coordinator will contact the patient by telephone. The patient will sign the e-consent form in a similar manner as the surrogate decision-maker e-consent procedures described above. If the patient does not have access to a computer, and the patient provides verbal permission, a paper informed consent form for the patient to sign and return, a blank copy for the patient to keep, and a stamped addressed envelope to return the signed copy will be mailed to the patient. If the patient is found capable and declines participation, the patient and surrogate will be immediately terminated from the study. Study staff will print a copy of the signed document, and give to participant at time of study visit. Should a participant choose to receive a link to the consent document in lieu of a hard copy (or if they sign electronically from a remote location), they will receive a link to a ROCKET site containing the consent form appropriate to the version date that they signed. Signed consent documents will NOT be housed electronically on ROCKET. No research procedures will be performed until after consent has been provided.

After written informed consent is provided by the patient or surrogate, baseline measures will be completed, and patients will then be randomized (stratified by treating hepatologist) to the control or intervention arm using validated computer programs (**see Figure 3**). If the surrogate decision-maker provided consent for

the patient, patients will be randomized, but baseline measures will be completed by the patient after providing written informed consent. A panel within the EMR containing all enrolled patients and the arm assignment will be created and shared with the PC team.

[figure not shown]

Figure 3. Approach for Study Participant Selection

Caregiver Participation

Patients will be asked to identify a primary caregiver to participate in the study. The identified caregiver may be the surrogate decision-maker. If the patient does not have a surrogate or if the patient prefers to name a different individual as the caregiver, he/she will be asked to identify a family member or close friend who is familiar with the patient's diagnoses and treatment, has daily or near daily contact with the patient in a variety of settings (home, hospital, etc.), and is someone the patient feels comfortable answering survey questions about his/her care. Written informed consent by the study participant for caregiver participation will be documented by separate signature on the main informed consent form. If the patient declines to name a caregiver or does not want the surrogate decision-maker to participate in this capacity, the patient will *not* be excluded from the study. The SC will approach the caregiver to explain the purpose of the study and the caregiver's role. If the caregiver agrees to participate, the SC will obtain the caregiver's written informed consent via the separate Caregiver e-consent or paper consent form in the same manner as described above. If the caregiver is not present on the hospital unit, the patient will be asked to provide contact information for the caregiver. The SC will contact the caregiver via telephone to obtain consent, in a similar manner as the procedures described above.

Caregiver participation includes the collection of demographic (**Appendix B**) and outcome data via a stress survey and satisfaction of care survey at specified time points (see Table 2).

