During the telephone contact, if a palliative care nurse identifies a need for further care (e.g., referral to hospice, appointment with the outpatient palliative care office, appointment for symptom management, etc.), the nurse will engage the palliative care team and/or the Hepatology team as indicated. Nurses will relay all relevant information from the telephone contacts to the palliative care team and the treating hepatologists via StarPanel and other clinically appropriate communication channels. If the patient is readmitted to the hospital, the inpatient in-person follow-up and outpatient telephone follow-up schedule will restart. Patients will receive inpatient consultations and follow-up outpatient telephone consultations for one year after randomization to the intervention arm or until death.

After completion of the one-year intervention phase, patient participation will be complete. With the exception of the follow-up telephone contacts and patient-friendly materials, similar services are available to all patients per routine practices. There are no other investigational agents or processes being used for the intervention group of patients/providers. See **Figure 4** below for trial design.

[figure not shown]

Figure 4. RCT Study Schema

The palliative care intervention is expected to include:

- Informational, patient friendly Palliative Care Binder, magnet, handout, wallet card
- Establishment of a palliative care plan
- Care coordination by palliative care team
- Early and regular ongoing engagement of palliative care physicians and nurse practitioners for inpatient consultations
- Telephone contacts conducted by trained palliative care nurses to review palliative care plan, assess changes in symptoms, identify patient needs and re-engage the palliative care team or Hepatology team as appropriate for referrals or appointments
- Communication by palliative care team to all providers and teams involved in patient's care
- Systematic collection of information, including identification of surrogate or health care proxy and advance care planning

Inpatient and telephone palliative care consults will consist of a systematic process utilizing standardized template forms and will include all of the components outlined in **Table 1**.

Table 1

Palliative Care Intervention Procedures	Inpatient In-Person Consults	Outpatient Telephone Consults
Introduction to PC	X	
Introduction to concepts of Advance Directive, living will, healthcare agent	X	

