- Patient mood
- Patient satisfaction with care
- Caregiver reported stress
- Caregiver reported satisfaction with patient care (including quality of death and dying, as applicable)
- Liver transplant status (deferred, listed, decline)
- MELD score
- Number of completed liver transplants
- Patient diagnoses and physical symptoms (e.g., presence of ascites, variceal bleeding, encephalopathy, delirium)
- Presence of Advance Directives (Goals of Care, Code Status, Surrogate decision-maker, etc.)
- Survival
- Staff satisfaction with intervention procedures

Process outcomes to measure intervention fidelity are expected to include:

- Number of responses to surprise question, number of 'No' responses to surprise question, number of patients with 'No' response to surprise question who are approved for enrollment
- Number of enrolled patients who receive the palliative care intervention
- Use of standardized forms by palliative care providers
- Clear documentation of a plan of care
- Concordance with goals of care (EMR derived, standardized, objective and measurable variables including DNR order non-adherence, aggressive treatment at end of life without expressed patient consent, CPR, mechanical ventilation, intubation, feeding tubes, re-admission, medications, etc.)
- Documented referrals/coordination with social workers or hospice when applicable
- Documented communication of Palliative Care Plan to patient's hepatology provider
- Completed Advance Directive, including designation of a Surrogate Decision Maker

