Aim 1: Time to first hospital readmission within 1-year post randomization will be compared across treatment assignment using Cox proportional hazards model, accounting for the competing risk of death and adjusting for relevant demographic and clinical characteristics. A less than 1 hazard ratio for the treatment group status implies reduced readmission rates in the intervention arm given equal mortality rates.

Aim 2: Days alive out of hospital within 6-months post randomization, total days in hospital and ICU within 1-year post randomization, number and cost of hospital admissions within 1-year post randomization, median length of stay per admission, number of transfers to hospice within 1-year post randomization, time to hospice placement after referral, survival, presence of advance directives within 1-year post randomization, presence of physical symptoms, transplant status listing (deferred, listed, declined), and number of completed liver transplants will be obtained via chart review and compared across treatment assignment using proportional odds model for ordinal outcomes, Cox proportional hazards model for time-to-event outcome and logistic regression for binary outcomes, adjusting for relevant demographic and clinical characteristics.

Aims 3 and 4: Both cross-sectional and longitudinal analysis will be conducted to compare between group differences in CLDQ. For the cross-sectional study, for each time point of data collection, linear regression with ordinary least square will be used with CLDQ as the dependent variable (DV) and treatment assignment (0 for control arm and 1 for the intervention arm) as the independent variable (IV) of interest adjusting for baseline CLDQ and potential confounding factors based on clinical and statistical considerations. A positive value of the regression parameter for treatment status indicates higher CLDQ in the intervention arm. For longitudinal analysis, linear mixed model will be adopted including follow-up time and the interaction between follow-up time and treatment group on top of the cross-sectional model. The interaction term is included to compare decreasing rate of CLDQ between groups with a positive value of the corresponding regression parameter indicating slower decline rate of CLDQ in the intervention arm.

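### The advance-directive outcome counts directives already charted before randomisation, which shrinks the arm difference by the unrecorded baseline share

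*Combined protocol and SAP*

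**What the plan says.** The protocol's secondary outcome list (section 6.0, Outcomes) contains "Presence of Advance Directives (Goals of Care, Code Status, Surrogate decision-maker, etc". Section 8.0, Aim 2, gives the outcome to be compared between arms as "presence of advance directives within 1-year post randomization". Neither place requires the directive to be new. Aim 2 adjusts for demographic and clinical characteristics that it does not name, and baseline directive status is not mentioned.

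Table 1 in section 6.0 includes review of directives completed earlier, so the protocol expects some patients to arrive with one.

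Entry is broad: "Any Vanderbilt patient admitted to the primary inpatient service of one of the study hepatologists with limited life expectancy may be eligible for participation". The five exclusions in section 5.0 cover age, consent, English, hepatology care elsewhere, and "Treating hepatologist denies permission to enroll". None refers to existing palliative care, hospice or directives. Section 6.0 adds: "With the exception of the follow-up telephone contacts and patient-friendly materials, similar services are available to all patients per routine practices".

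**The concern.** A patient who enters with a directive scores as a success whichever arm is assigned. Such patients add equally to both arms and carry no information on whether the intervention leads people to complete directives. Advance care planning is a core part of the intervention, and this outcome is where an effect on it would appear. If many patients already have a directive, code status or named surrogate on the chart, a real effect could be missed.

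A related gap is that palliative care and hospice status at entry is not listed among the data to be collected. Section 1.0 names contamination of control groups among possible reasons for mixed results in earlier palliative care trials. As written, the plan could not show how much prior exposure this trial had.

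**Working it through.** **Advance directives: inputs.** There are 200 patients per arm (section 5.0) and α = 0.05 (section 8.0), taken as two-sided. The plan states no power for this outcome, so there is no figure to reproduce. Three quantities are assumptions:
- new completion among patients without a directive: c₀ = 30% under usual care and c₁ = 45% under intervention;
- baseline share q, varied;
- no change to directives already in place.

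Section 1.0 gives two figures for scale only. DNR status was 28% in patients removed from the transplant list or declined, and 16% (8 of 51) in patients with cirrhosis in another study. Neither is a directive rate at entry to this trial.

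**Formulas.**
- Presence: p = q + (1 − q)c, so the difference is (1 − q)(c₁ − c₀).
- New directives among all patients: p = (1 − q)c. The difference is again (1 − q)(c₁ − c₀).
- New directives among patients without one at baseline: c₁ − c₀, with n = 200(1 − q) per arm.
- Power = Φ{[d − 1.96√(2p̄(1 − p̄)/n)] / √[(p₀(1 − p₀) + p₁(1 − p₁))/n]}.

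**Worked case, q = 28%.**
- Presence: p₀ = 0.28 + 0.72 × 0.30 = 0.496 and p₁ = 0.28 + 0.72 × 0.45 = 0.604, so d = 0.108. Power = Φ[(0.108 − 1.96 × 0.0498)/0.0495] = 58%.
- New, all patients: 0.216 versus 0.324, d = 0.108, power 68%.
- New, those without one at baseline: 0.30 versus 0.45, n = 144 per arm, d = 0.15, power 75%.

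| q | Difference in presence (points) | Power, presence | Power, new among all | Power, those without one |
|---|---|---|---|---|
| 0% | 15.0 | 88% | 88% | 88% |
| 16% | 12.6 | 72% | 78% | 81% |
| 28% | 10.8 | 58% | 68% | 75% |
| 50% | 7.5 | 37% | 49% | 59% |

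Counting only new directives leaves the absolute difference diluted by the same factor. Its power gain here also depends on completion being low. Per patient, its variance exceeds that of presence by q(1 − q)(2c − 1), which is negative when c is below 50% and positive above. Baseline adjustment or restriction is therefore needed.

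**Primary outcome: worst case only.** Table 3 reproduces. With 400 × R events and (1.960 + 0.842)² = 7.85, solving 400R[(1 − HR)/(1 + HR)]² = 7.85 gives HR 0.669, 0.694, 0.713, 0.729 and 0.743 for R = 50% to 90%. These match the five stated values after rounding. At R = 60% and HR 0.69, readmission under intervention is 1 − 0.40^0.69 = 46.9%, a 13.1-point difference. Power is Φ(½√240 × |ln 0.69| − 1.96) = 82.0%.

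Now suppose a share q of both arms already has palliative care and gains nothing further. The difference becomes 13.1 × (1 − q), and the effective HR is ln(1 − p₁)/ln(0.40), where p₁ is 60% minus that difference.

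| q (assumed) | Difference (points) | Effective HR | Power |
|---|---|---|---|
| 5% | 12.5 | 0.70 | 78% |
| 11% | 11.7 | 0.72 | 72% |
| 20% | 10.5 | 0.75 | 62% |

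The 11% is the palliative referral rate in the transplant-denied cohort of section 1.0 and is used only for scale.

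**The case against.** The strongest reply is that this is one unpowered secondary outcome, that randomisation balances baseline status on average, and that the unnamed clinical covariates in Aim 2 could include directive status. All three points are fair. They limit the matter to loss of precision in a secondary result, and they show how cheap the remedy is. They do not remove it, because an unnamed covariate that nobody is told to abstract may not exist at analysis.

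Four stronger readings are tempting, and the documents do not support them.
- **The hospice count includes earlier transfers.** It does not. Sections 2.0, 6.0 and 8.0 limit it to transfers in the year after randomisation. A narrower gap remains: no rule covers a patient referred or enrolled before randomisation, and time to hospice has no origin in section 6.0 but runs from referral in section 8.0.
- **The primary analysis is underpowered through prior palliative care.** This needs a prevalence that the documents do not give and zero further benefit. Section 6.0 says the telephone contacts are not routine, and they run at least monthly, so they would be new to these patients. Section 1.0 also describes palliative care in this population as usually late.
- **Such patients should be excluded.** The comparator allows palliative care on request, and Aim 5 concerns generalisability. Enrolling whoever presents fits both. Hepatologist refusal may remove some of these patients, though no criteria are given.
- **Seeking consent creates the surrogate outcome.** Section 5.0 says "The patient's surrogate decision-maker will also be approached to provide consent for the study", but nothing shows that research consent produces a charted designation. Naming a surrogate is an intervention component in Table 1, so dropping it would discard a targeted effect.

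Figure 3 (participant selection) was not available in the copy reviewed, so an added screening step there cannot be ruled out.

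**Conclusion.** The point holds for the advance-directive outcome. As written, presence within a year credits both arms with directives that predate randomisation and shrinks the absolute difference by exactly (1 − q), provided existing directives stay in place. This is attenuation and not bias between arms. Its size is unknown because q is not documented. Under the assumed 30% versus 45% completion, power falls from 88% to between 72% and 37% as q runs from 16% to 50%. At q = 28%, restricting to patients without a directive at entry recovers power from 58% to 75% and restores the 15-point difference.

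For the primary and hospice outcomes, the documents support only a request to record prior exposure and test sensitivity to it. The primary power range of 78% to 62% is a worst case for assumed shares of 5% to 20%, not an estimate.

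**What to change.** 1. In the planned chart review, abstract directive status at randomisation by component: directive, code status, named surrogate.
2. Define the outcome as a directive first completed or changed after randomisation. Keep surrogate naming as a component, counted only when newly charted after randomisation.
3. Name baseline directive status as a covariate in the Aim 2 model, or prespecify the analysis among patients without a directive at baseline.
4. Record palliative care and hospice status at baseline. Prespecify a sensitivity analysis of the primary and hospice outcomes without patients already under, or referred to, these services. Do not add an exclusion.

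For directives the cost is one more abstracted field and a few lines of analysis text. Item 4 adds baseline palliative care and hospice status to a record review that section 5.0 already requires for eligibility. Neither sample size nor accrual changes. These definitions should be fixed before outcome data are seen by arm, since a baseline rule written later would look post hoc.
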